From the time of obtaining informed consent through the first administration of study drug, record all SAEs, as well as any AEs related to protocol-mandated procedures on the adverse events electronic case report form (eCRF). All other untoward medical occurrences observed during the screening period, including exacerbation or changes in medical history are to be captured on the medical history eCRF. See Section 7 Adverse Events and Toxicity Management for additional details.

6.3. Treatment Assessments Blinded Phase (Weeks 4, 12, and Every 12 Weeks Until the end of blinded treatment phase visit)

The following evaluations are to be completed at the Weeks 4, 12, and every 12 weeks visits until the end of blinded treatment phase visit unless otherwise specified.

All study visits are to be scheduled relative to the Day 1 visit date. Study visits are to be completed within ± 2 days of the protocol-specified visit date based on the Day 1 visit through Week 12 and study visits thereafter completed within ± 14 days of the protocol-specified visit date through the end of blinded treatment phase visit, unless otherwise specified.

Regularly scheduled evaluations will be performed for all participants whether or not they continue to receive study drug, unless otherwise specified.

- Targeted (symptom directed) physical examination (complete physical examination at Weeks 48 and 96 only)
- Review of AEs and changes in concomitant medications, including assessment of whether any STIs were diagnosed and any treatments were received since last visit
- When clinically indicated, vital signs measurement (blood pressure, pulse, respiration rate, and temperature)

- Weight
- STI testing. Participants who test positive for any STI will be treated in accordance with local STI guidelines.
 - Genital, rectal, and pharyngeal examination as appropriate
 - Pharyngeal and rectal swabs for gonorrhea and chlamydia (per local lab). Swabs may be self-administered by the participant at the discretion of the investigator (rectal swab not required at Week 4).
 - Urine sample for gonorrhea and chlamydia (per central lab)
 - Blood sample for syphilis testing (per local lab)
- Fourth generation rapid HIV-1 Ab/Ag or third generation rapid HIV-1 Ab test (**not done for HIV-infected participants**)

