## • For postbaseline visits:

For BMD data, the record(s) collected on the latest day in the window will be selected for analysis.

For CASI Follow-Up questionnaires, the record(s) collected on the day closest to the nominal day for that visit will be selected. If there are 2 days equidistant from the nominal day, the later day will be selected. Additionally, as some subjects retrospectively completed CASI questionnaires for previous missed visits, when multiple record(s) occur on the same day, the record with a subject assigned visit week equal to the analysis window visit week defined in Section 3.8.2 will be selected.

For Week 4 PK and PBMC trough samples, analysis windows will not be applied, but only samples labeled as a 'trough' collection will be selected. For anytime PK samples, only samples labeled as an 'anytime' collection will be selected and the rules below for other numeric observations applied.

For other numeric observations (ie, except BMD, CASI and Week 4 trough specified above), the record(s) collected on the day closest to the nominal day for that visit will be selected. If there are 2 days equidistant from the nominal day, the later day will be selected.

For any numeric observations, if there are multiple records on the selected day, the average will be taken.

If multiple valid nonmissing categorical measurements exist in a window, records will be chosen as follows:

- For baseline, the last available record on or prior to the first dose date of study drug will be selected. If there are multiple records with the same time or no time recorded on the same day, the value with the lowest severity will be selected (ie, normal will be selected over abnormal) except for gonorrhea and chlamydia laboratory STIs where the worst severity value will be selected (ie, abnormal will be selected over normal).
- For postbaseline visits, the worst severity value within the window will be selected (ie, abnormal will be selected over normal).

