### 4.2.3.2. Adherence to Study Drug Regimen While On-Treatment via Self Report

For the DB phase, adherence to study drug while on-treatment via patient self-report from the CASI follow-up questionnaire data will be summarized by visit from the question: "Approximately how many doses (days) of PrEP tablets have you missed since your last study visit?"

Adherence rates will be calculated based on the number of pills taken divided by the number of days between visits. The number of pills taken is the number of days between visits minus the number of doses (days) of PrEP tablets missed. The number of days between visits is based on 28 days between Day 1 and Week 4, 56 days between Week 4 and Week 12 and 84 days between

visits starting on Week 24 and later. Each subject and visit combinations' minimum adherence rate will be capped at 0%. On-treatment data includes visits occurring through the upper limit of the analysis window corresponding to the date of permanent discontinuation of study drug for subjects that permanently discontinued study drug or all available postbaseline data for subjects who were still on study drug.

By visit descriptive statistics for the adherence rate based on the number of pills missed (n, mean, SD, median, Q1, Q3, minimum, and maximum) along with the number and percentage of subjects in adherence categories based on missing the following number of pills (or days) will be summarized.

Table 4-1. Adherence Rates from Number of Doses (Days) of PrEP Tablets Missed in CASI

Adherence rate approximation	Week 4	Week 12	Week 24 and later visits
< 30% adherence	≥ 20 days	≥ 40 days	≥ 59 days
≥ 30% to < 60% adherence	≥ 12 to ≤ 19 days	$\geq$ 23 days to $\leq$ 39 days	$\geq$ 34 days to $\leq$ 58 days
≥ 60% to < 80% adherence	≥ 6 to ≤ 11 days	$\geq$ 12 days to $\leq$ 22 days	$\geq$ 17 days to $\leq$ 33 days
≥ 80% to < 90% adherence	$\geq 3$ to $\leq 5$ days	≥ 6 to ≤ 11 days	≥ 9 to ≤ 16 days
≥ 90% to < 95% adherence	2 days	$\geq$ 3 to $\leq$ 5 days	$\geq$ 5 to $\leq$ 8 days
≥ 95% adherence	≤ 1 day	≤ 2 days	≤ 4 days

Approximate adherence rates are based on 28 pills prescribed for 28 days between Day 1 and Week 4, 56 pills prescribed for 56 days between Week 4 and Week 12 and 84 pills prescribed for 84 days between visits starting on Week 24 and later.

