# 9.3. Anal Intercourse Partners While At Risk of HIV Infection During the DB phase (CASI Questionnaire)

The number of anal intercourse partners from CASI questionnaire responses will be summarized by treatment group and visit while at risk of HIV infection during the study, using descriptive statistics (n, mean, SD, median, Q1, Q3, minimum, and maximum) as well as the number and percentage of subjects with 0, 1, 2, 3, 4-5, 6-10 and  $\geq$  11 partners on the FAS. The following summaries of number of anal intercourse partners will be provided:

- Unprotected Receptive Anal Intercourse (URAI) Partners
- Unprotected Insertive Anal Intercourse (UIAI) Partners
- Anal Intercourse Partners

While at risk of HIV infection during the study includes visits occurring through the upper limit of the analysis window corresponding to the last at-risk of HIV infection date as defined in Section 6.2.3.

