- 19) For prescribed adherence based on pill counts (Section 4.2.3.1), any bottles dispensed after the end date would not be counted into the adherence calculation.
- 20) LOCF and BIOCF will not be applied at a visit for a subject who is both missing on-treatment values at a visit and has not reached the upper limit of the analysis window for that corresponding visit. For the determination of whether a subject has reached the upper limit of the analysis window, the (1) lab transfer date for lab parameters or (2) DXA transfer date for BMD values will be compared to the upper limit of the analysis window.
- 21) For CASI summaries of
  - a) Adherence while on on-treatment (through the last dose date) includes all visits for subjects that are ongoing on study drug and visits occurring through the upper limit of the analysis window corresponding to the date of permanent discontinuation of study drug for subjects that permanently discontinued study drug. (ie. if the last dose date is Day 250, this falls in the Week 36 analysis window and all CASI visits through Day 294 will be included.)
  - b) Intercourse partners while at risk of HIV infection (through the last at-risk of HIV infection date) includes visits occurring through the upper limit of the analysis window corresponding to the last at-risk of HIV infection date for each subject.

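### The on-treatment self-reported adherence summary admits questionnaires after the last dose, so an off-drug report can replace the discontinuation-visit report that already covers the final on-drug interval

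*SAP*

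**What the plan says.** SAP Appendix 12, item 21(a) opens by defining "Adherence while on on-treatment (through the last dose date"), and then includes "visits occurring through the upper limit of the analysis window corresponding to the date of permanent discontinuation of study drug". Its own example reads "last dose date is Day 250, this falls in the Week 36 analysis window and all CASI visits through Day 294 will be included". SAP 4.2.3.2 carries the same window rule: "On-treatment data includes visits occurring through the upper limit of the analysis window corresponding to the date of permanent discontinuation of study drug".

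SAP 9.3 and item 21(b) treat partner counts in the same way, taking "visits occurring through the upper limit of the analysis window corresponding to the last at-risk of HIV infection date". For a participant diagnosed with HIV, that date is the diagnosis date (SAP 3.8.1 and 6.2.3).

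Where a window holds more than one follow-up questionnaire, SAP 3.8.3 says "the record(s) collected on the day closest to the nominal day for that visit will be selected", with the later day taken if two are equally distant.

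Off-drug questionnaires will exist. Protocol 6.3 states: "Regularly scheduled evaluations will be performed for all participants whether or not they continue to receive study drug". Its CASI item has no exemption for people off drug, whereas the drug accountability and dispensing items beside it do. CASI is also done at the ESDD visit, which is requested within 72 hours of stopping (Protocol 6.7.1).

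**The concern.** Item 21(a) gives two end points for one summary: the last dose date and the end of the window containing it. The second lets in questionnaires completed wholly off drug.

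The selection rule makes this more than a loose label. The adherence question asks about doses missed since the last study visit. Once an ESDD questionnaire has been completed, the next scheduled one looks back only to the ESDD visit, so its whole recall period is off drug. If it lies closer to the nominal day, it becomes the on-treatment value, and the report that covers the final on-drug interval drops out of the table.

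For partner counts the parallel issue is that behaviour reported after an HIV diagnosis can be tabulated as behaviour while at risk.

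**Working it through.** **Inputs.** Windows: SAP Table 3-1 (Week 4, Days 2–56; Week 12, Days 57–126; Week 36, Days 211–294; later windows also 84 days wide). Visit tolerance: ±14 days after Week 12 (Protocol 6.3). ESDD visit: within 72 hours of stopping. Score: (interval − missed days) / interval, with the interval fixed at 84 days from Week 24 onward (SAP 4.2.3.2). Selection: closest to nominal, later if tied (SAP 3.8.3).

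**The plan's own example.** Upper limit of Week 36 = (36 + 6) × 7 = Day 294. A last dose on Day 250 lies in Days 211–294, so records are kept to Day 294, which is 294 − 250 = 44 days off drug. This agrees with item 21(a).

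**Largest lag allowed.**
- Week 4: 56 − 2 = 54 days.
- Week 12: 126 − 57 = 69 days.
- Week 24 onward: for example 294 − 211 = 83 days.
- On-schedule visit, Week 24 onward: (252 + 14) − 211 = 55 days. Reaching 83 needs a late, unscheduled or end-of-blinded-phase questionnaire.

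**One record.** Last dose on Day 215, ESDD questionnaire on Day 217 with no missed doses, scheduled questionnaire on Day 252. Distances from nominal Day 252 are 35 and 0, so Day 252 is selected. It covers 252 − 217 = 35 days, all off drug.
- If those days are reported as missed: (84 − 35) / 84 = 58%, in the 30% to under 60% band of Table 4-1.
- If none is reported as missed: 84 / 84 = 100%, for an interval in which no drug was taken.

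**How often.** This is a simulation of participants who stop in an 84-day window and stay on study. Assumptions: stop day uniform over Days 211–294; scheduled visit Day 252 ± 14, uniform; ESDD questionnaire always completed, 0 to 3 days after stopping.

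| Quantity | Result |
|---|---|
| Scheduled questionnaire after the last dose | 49% |
| It displaces the ESDD record | 39% |
| Mean off-drug days in the displacing record | about 24 |
| Mean score of displacing records, if off-drug days are reported as missed | 72% |
| Displacing records scoring below 80%, same assumption | 68% |

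As a share of all such stoppers, 0.39 × 0.68 = about 27% would score below 80%, again only under the reporting assumption.

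**Stoppers with no ESDD questionnaire.** With the same assumptions and the previous visit at Day 168 ± 14, the first scheduled questionnaire after stopping covers about 64 on-drug and 22 off-drug days on average. About 93% of these records fall more than 3 days after the last dose.

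**The case against.** The strongest defence is that the question looks back. For someone who misses the ESDD visit, which participants are only asked to attend, the first questionnaire after stopping is the only record of the final on-drug interval, and a window-end rule retains it. This stands. A flat cut at the last dose plus 3 days would discard about 93% of such records, selectively among stoppers. Last dose dates are also sometimes imputed (SAP 3.8.1; Appendix 12, item 14), so a strict date cut could delete a genuine ESDD questionnaire. Both points argue for a narrower fix. Neither justifies preferring a wholly off-drug record when an ESDD record exists.

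A reader might also infer that fully adherent people are necessarily placed in low adherence categories. The documents do not support that. They do not say how someone off drug should answer, and the full questionnaire is not included. Another missed-tablet item can be set to not applicable (Appendix 12, item 34). An answer of none missed scores 100%, so the direction of bias is open.

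The partner-count issue is narrow. For uninfected participants the at-risk period ends at the last HIV test, and HIV tests and CASI share the scheduled visits. The matter concerns mainly infected participants.

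**Conclusion.** The point holds in limited form. The label and the rule in item 21(a) disagree, and the rule combined with closest-to-nominal selection can report a wholly off-drug interval as on-treatment adherence. The lag is at most 55 days for an on-schedule visit from Week 24 onward and 83 days at the extreme. Under the stated assumptions, displacement affects about 39% of on-study stoppers whose last dose falls in such a window. The 58% and 72% scores rest further on off-drug days being reported as missed.

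A reader might infer a bias between arms or an effect on the efficacy result. Neither is shown. Data after the first open-label dose are excluded from double-blind summaries (SAP 3), so mainly premature discontinuers who remain on study are affected, and the effect on an arm's mean is small. No figure in the documents indicates a difference between arms. The summaries are descriptive and do not enter the rate ratio (SAP 6.2.5). Adherence is not a per-protocol criterion (SAP 6.3), and it is also measured by pill count and dried blood spots (SAP 4.2.3). This is a worthwhile tidy-up that threatens no main conclusion.

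**What to change.** Apply these conditions before record selection, in SAP 4.2.3.2, SAP 9.3 and Appendix 12 item 21.

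- **Adherence, with a questionnaire dated from the last dose date to 3 days after it:** exclude later questionnaires from the on-treatment summary.
- **Adherence, with no such questionnaire:** keep only the first one after the last dose, and flag it as partly off-drug. Where the last dose date was imputed too early, this also keeps a genuine ESDD record.
- **Partner counts, infected participants:** keep records up to and including the first questionnaire on or after the diagnosis date, and exclude later ones. That first record looks back over the interval in which infection was found. A cut with no tolerance could lose it, because the diagnosis date is set retrospectively to the earliest positive result (SAP 6.2.2).
- **Labels:** align the last-dose wording in item 21(a) and the last at-risk wording in item 21(b) with these rules.

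The cost is minor programming. A partly off-drug interval remains for stoppers without an ESDD questionnaire, but it is identified as such.

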#### **22) TEAE**

# **Events with Missing Onset Day and/or Month**

An AE is treatment emergent if the following 3 criteria are met:

- 1) The month and year (or year) of onset date is the same as or after the month and year (or year) of the first dose of study drug, and
- 2) The month and year (or year) of the onset date is the same as or before the month and year (or year) of the 30th day after the date of the last dose of study drug, and
- 3) End date is as follows:
  - a) The (complete) end date is on or after the first dose date, or
  - b) The month and year (or year) of end date is the same or after the month and year (or year) of the first dose of study drug, or
  - c) End date is completely missing or AE is ongoing

# **Events with Completely Missing Onset Date**

An AE with a completely missing onset date is defined as TEAE if end date meets any of the criteria specified in 3) above.

23) TEAE incidence rate and prevalence rate:

If the AE onset date or stop date is incomplete and not ongoing, then day will be imputed as the 15th of the month when only month and year are available and the day and month will be imputed as July 1st when only year is available. The imputed AE end date will be refined as the maximum of (AE onset date, imputed AE end date). The imputed AE onset date will be refined as the minimum of (the maximum of [first dose date, imputed AE onset date], AE stop date).

If the AE stop date is unknown (both AE stop date and ongoing status are missing even after query) or ongoing, the AE end date will be imputed with the last dose date.

- 24) Renal related laboratory ratios were calculated at Covance, but recalculated at Gilead in order to increase the decimal place precision to match those previously reported in other Gilead HIV treatment studies.
  - a) Differences in the computation methods between Covance and Gilead, respectively, include:
    - i) renal ratios computed using SI units in EU sites which were converted to conventional (CNV) units (Covance) vs. renal ratios computed using only CNV units (Gilead)
    - ii) for urine creatinine in the computation of renal ratios, use of original unrounded instrument values (Covance) vs. rounded reported Covance values (Gilead)
    - iii) differences in handling of < LOQ values for the individual lab components used to compute the ratios.

Further details are outlined below.

# Differences in the Handling of the Individual Lab Components Used for the Computation of the Renal Ratios

Differences	Covance Computed	Gilead Computed
Units	North American accession numbers (beginning with '65'): uses component values in conventional units to compute renal ratios  EU accession numbers (beginning with '62'): uses component values in SI units to compute renal ratios then applies a conversion factor to convert the creatinine SI units into conventional units (0.00884 mmol/mg)  For urine Beta 2 microglobulin to creatinine ratio, the mg/mmol SI units were converted to mg/mg conventional units by multiplying by 0.00884. ie. Urine Beta 2 microglobulin (mg/L) / creatinine (mmol/L)  1 mg/mmol x 0.00884 mmol/mg 0.00884 mg/mg  For UPCR, the mg/mmol SI units were converted to conventional units by multiplying by 0.00884 ie. [ Urine protein (mg/dL) / creatinine (mmol/L) ] x 10 dL/L  10 mg/mmol x 0.00884 mmol/mg 10 x 0.00884 mg/mg  For Urine RBP to creatinine ratio, the ug/mmol SI units were converted to conventional units by multiplying by 0.00884 ie. Urine RBP (ug/L) / creatinine (mmol/L) 1 ug/mmol x 0.00884 mmol/mg (1/1000) x 0.00884 mmol/mg	Uses component values in conventional units to compute renal ratios
Rounded values for urine creatinine	Uses measured unrounded result from the instrument 2 decimal places in mg/dL (CNV) 3 decimal places in mmol/L (SI)	Uses the rounded result reported in Covance datasets  0 decimal places in mg/dL (CNV) 2 decimal places in mmol/L (SI)
Imputations for < LOQ	Uses LOQ values in the calculation of related ratios and reapplies the < sign to the final value.	For urine creatinine, values of "< 1" are handled as missing values in the calculation of related ratios.  For urine RBP (ug/L), values of "<18.000" are treated as 17.999 in the calculation of renal ratios. For urine Beta 2 microglobulin (mg/L), values of "<0.010" are treated as .009 in the calculation of renal ratios.
UPCR	Calculated for all subjects, even when urine protein < 4.0 mg/dL	Only calculated when urine protein ≥ 4.0 mg/dL

- b) Renal related laboratory evaluation (Gilead- computed values)
  - i) Unit conversion for renal safety tests derived from related tests with conventional units
  - Urine RBP (ug/L) to creatinine (mg/dL) ratio:  $1 (ug/L) / (mg/dL) = 100 \times ug/g$
  - Urine Beta-2-microglobulin (mg/L) to creatinine (mg/dL) ratio: 1 (mg/L) / (mg/dL) 10^5 ug/g
  - ii) Calculation of ratios:

To calculate laboratory ratios (ie, urine RBP to creatinine ratio), the lab value of each test in the ratio needs to be from the same accession number; if any test value used for the ratio calculation from the same accession number is missing, then the ratio is not calculable (ie, missing).-For urine creatinine, a value of "< 1" is handled as a missing value in the calculation of related ratios. For urine protein, a value of "< 4.0" is handled as a missing value in the calculation of UPCR.

- iii) Summary tables will be based on Gilead-calculated ratios.
- iv) Listings will include both Gilead-calculated and Covance-calculated ratios
- 25) Combined category of UP and UPCR (Gilead computed)
  - a) First merge UP and UPCR based on the subject identifier and accession number (prior to any application of LOCF or BIOCF).
  - b) At each visit, use UP to select which pair of records should be used for the analysis. That is, once a UP record is selected for that visit, the UPCR with the same accession number will be selected.
  - c) The baseline value will be the last nonmissing value on or prior to the first dosing date of study drug. If multiple measurements occur on the same day, the last nonmissing value prior to the time of first dosin
  - d) g of study drug will be considered as the baseline value. If these multiple measurements occur at the same time or the time is not available, the lowest severity (UPCR  $\leq$  200 mg/g) will be taken or if severity is also the same the later clinical visit will be taken.
  - e) The postbaseline record(s) collected on the day closest to the nominal day for that visit will be selected. If there are 2 days equidistant from the nominal day, the later day will be selected. If there are multiple records on the selected day, the worse severity (UPCR > 200 mg/g) will be taken or if severity is also the same the later clinical visit will be taken.

